English Synopsis

I. Title of Study

Effect of non-nutritive sucking on feeding intolerance in premature Infants

II. Indication

To study the effect of non-nutritive sucking on feeding intolerance in premature infants.

III. Phase of Development:

This is a study for a master thesis. Not applicable.

IV. Study Rationale:

Premature babies are defined as babies born alive before 37 weeks of pregnancy. There was 10.5% preterm of whole pregnancy in Taiwan, including 9.14% low birth weight (LBW) who born weighting between 1500-2499 g and 1.02% very low birth weight (VLBW) who born weighing under 1500 g. Generally, more early gestational ages and lower birth weight accompany more problems. They need to accept professional supervision, monitoring, and caring to maintain their growth in the neonatal intensive care unit (NICU). Premature infants need a progressive nasogastric tube diet to meet their nutritional needs due to the immature gastrointestinal tract. However, feeding intolerance, such as gastric residual volume (GRV), meteorism, and milk regurgitation, is also increased due to an immature, less functional gastrointestinal tract. This symptom will result in less feeding or fasting, which makes premature infants cannot get enough enteral nutrition and extrauterine growth restriction (EUGR). Although there is no standard guideline for relieving feeding intolerance symptoms and providing enough nutrients until now, non-nutritive sucking (NNS) was thought to have the benefit premature infants. It can stabilize an infant's emotions, and physiological condition, relieve pain, promote the development of sucking, increase the efficacy of oral feeding, decrease the time of nasogastric tube feeding and shorten the hospital stay. This study wants to evaluate whether the different times of NNS before feeding can decrease the incidence of feeding intolerance.

V. Study Objectives:

To evaluate whether non-nutritive sucking before oral feeding can reduce the feeding intolerance, such as gastric residual volume (GRV), meteorism, and

milk regurgitation.

VI. Study Design

- Duration of Treatment
3 days

- Number of Planned Patients
180 participants, 146 evaluable participants.
 - Birth between Week (26-27)+6 days:
Experiment A group:30, Experiment B group:30, Control group: 30
 - Birth between Week (28-31)+6 days, above :
Experiment A group:30, Experiment B group:30, Control group: 30

- Investigational Product
Not applicable.

- Endpoints
Primary endpoint:
To evaluate whether non-nutritive sucking before oral feeding can reduce the feeding intolerance, such as gastric residual volume (GRV), meteorism, and milk regurgitation, compared to no intervention.

Secondary endpoint:
To evaluate whether 5 minutes of non-nutritive sucking before oral feeding can reduce the feeding intolerance, such as gastric residual volume (GRV), meteorism, and milk regurgitation, better than 15 minutes of non-nutritive sucking before oral feeding.

- Criteria for Evaluation
The full analysis set (FAS) means all the data of a participant was collected and an intent-to-treat set (ITT) means data of a participant with at least 4 interventions was collected. The primary and secondary endpoints will be analyzed by a FAS and an ITT.

- **Statistical Methods**

For the primary and secondary endpoint, all the data will be checked their normal distribution by Kolmogorov-Smirnov analysis to determine whether to use parametric or nonparametric statistics. The difference in gastric residual volume (GRV), meteorism, and milk regurgitation between the NNS intervention and no intervention will be analyzed by the generalized estimating equations of SPSS 21, α value will be set at 0.05.

- **Duration of the Study**

2022/07/01 to 2024/06/30, a total of 2 years.

- **End of Study**

The sponsor reserves the right to terminate the study, according to the master thesis progression. The sponsor may terminate the study due to the following situations:

- i. The master thesis topic is changed.
- ii. The data show a significant result to the hypothesis, although the recruited number does not reach 180.

The investigator should notify the IRB in writing of the study's completion or early termination and send a copy of the notification to the sponsor.

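### The protocol asks one primary question but analyses three outcomes in two analysis sets at one alpha of 0.05, with no rule for which result decides success or ends the study.

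*Protocol*

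**What the plan says.** All of this is in section VI of the Protocol, Study Design, unless noted.

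- **Endpoints.** The primary endpoint is whether NNS can "reduce the feeding intolerance, such as gastric residual volume (GRV), meteorism, and milk regurgitation, compared to no intervention". No outcome is ranked first, and no combination rule is given.
- **Statistical Methods.** "The difference in gastric residual volume (GRV), meteorism, and milk regurgitation between the NNS intervention and no intervention will be analyzed" by generalized estimating equations, and "α value will be set at 0.05". Whether this is one-sided or two-sided is not stated.
- **Criteria for Evaluation.** "The primary and secondary endpoints will be analyzed by a FAS and an ITT". Neither set is named as the main one.
- **End of Study.** One permitted reason for termination is: "The data show a significant result to the hypothesis, although the recruited number does not reach 180". The hypothesis is referred to in the singular, without naming an outcome or a set.
- **Study Rationale (section IV).** The aim is put as "whether the different times of NNS before feeding can decrease the incidence of feeding intolerance", which could be read as a single combined outcome.
- **Number of Planned Patients.** In each of two gestational-age strata: "Experiment A group:30, Experiment B group:30, Control group: 30". The total is "180 participants, 146 evaluable participants".

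**The concern.** One question is posed, but three outcomes in two sets give up to six primary results, even with both NNS arms pooled against control. The protocol does not say whether one favourable result is enough, whether all three are needed, or whether the outcomes are to be combined.

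As written, a single significant outcome in either set could be reported as showing that NNS reduces feeding intolerance. The same result could be used to end the study before 180 infants are recruited. If the decision rule is settled only after the results are known, the nominal 0.05 no longer describes the risk of a false claim.

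An analysis plan could hold the details of a multiplicity adjustment. The primary endpoint and the termination trigger, however, are set in the protocol, and the trigger relies on a success event that the protocol does not define.

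**Working it through.** The protocol gives alpha as an input and derives no overall error rate, so it has no figure of its own to reproduce. The question is what error follows from each reading.

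**Inputs**
- Alpha 0.05 (Statistical Methods). Two-sided is assumed, which gives 0.025 per test in the direction of benefit. The one-sided case is shown as well.
- Three outcomes (Statistical Methods).
- One NNS-versus-control comparison per outcome, with A and B pooled. Assumed from the wording of Statistical Methods, which sets NNS against no intervention.
- Correlation r between the three test statistics: not in the documents. Assumed equal for all pairs and varied from 0 to 0.95.

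**Any one of three counts, one set**

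At r = 0: 1 − (1 − 0.025)³ = 1 − 0.9269 = 0.0731.

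For r > 0: 1 − ∫ φ(u) · [Φ((c − √r·u)/√(1 − r))]³ du, integrated numerically, with c = 1.960 (c = 1.645 if 0.05 is one-sided).

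| r | False claim of benefit, 0.05 two-sided (single test 2.5%) | Same, 0.05 one-sided (single test 5%) |
|---|---|---|
| 0 | 7.3% | 14.3% |
| 0.3 | 6.8% | 13.0% |
| 0.5 | 6.3% | 11.8% |
| 0.7 | 5.5% | 10.3% |
| 0.9 | 4.2% | 8.0% |
| 0.95 | 3.7% | 7.1% |

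**Other readings, one set, two-sided 0.05**
- One combined outcome: one test, so 2.5%.
- All three required: never above 2.5%. Under the same model it is 0.002% at r = 0 and 1.1% at r = 0.9.

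**Either set counts**

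A second chance of success cannot lower the error, and it raises it whenever the two sets differ. The size of the rise depends on how far the FAS and ITT overlap, which the documents do not give.

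**Holm in one decisive set, no outcome affected**

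The smallest p is compared with 0.05/3 = 0.0167 (z = 2.394). The chance of any false claim of benefit is 1 − (1 − 0.00833)³ = 2.5% at r = 0, and 1.5% at r = 0.9.

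**Power cost of Holm**

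The protocol states no power, so 80% is hypothetical. Power of 80% at two-sided 0.05 means an expected z of 1.960 + 0.842 = 2.802.
- First step (0.0167): Φ(2.802 − 2.394) = Φ(0.408) = 66%.
- Second step (0.025, z = 2.241): Φ(2.802 − 2.241) = Φ(0.561) = 71%.
- Last step (0.05): 80%.

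**The case against.** **The inflation depends on a rule the protocol never states.** This stands. The singular hypothesis in End of Study and the Rationale's reference to incidence leave a combined outcome open, and under that reading, or if all three are required, one set shows no inflation. A reader might infer that the trial will run at 7.3%. The documents support only a conditional statement. What is established is that the decision rule is missing.

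**The range is not a bound.** This also stands. It rests on assumed correlations and an assumed two-sided test; hence the 0.95 row and the one-sided column.

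**The two-set error can be calculated from 146/180.** A reader might take 146 evaluable out of 180 planned (81%) as the overlap of the two sets and so obtain a ceiling. Nothing in the protocol ties those numbers to the FAS and ITT. A smaller overlap also gives a higher error: with any one outcome in either set counting, independent outcomes and differences in either direction, it is 19.7% at 81% overlap and 22.9% at 50%. It is also unclear how control infants meet an ITT definition based on interventions received, so one set may not lie inside the other. No two-set figure is relied on here.

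**The list is already closed.** Largely right: Statistical Methods names exactly three outcomes without 'such as'. The endpoint wording needs aligning, but an unlimited choice of outcomes is not shown.

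**This belongs in the SAP.** True of the adjustment method and, commonly, of the choice of main set. It does not answer a protocol that sets the primary endpoint and makes termination depend on a result it does not define.

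**Holm is one choice among several.** Agreed. A single primary outcome, a combined outcome or an all-three rule would also control the error in one set. What matters is fixing one in advance.

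**Conclusion.** The point holds as a missing success rule, not as a demonstrated error rate. One primary question is served by three outcomes in two sets at one alpha, and the study may be ended on a result whose meaning is not fixed.

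If any one outcome suffices, a false claim of benefit in one set is about 1.5 to 3 times as likely as with a single test (3.7/2.5 = 1.5; 7.3/2.5 = 2.9) for correlations from 0.95 down to 0. That rests on a two-sided 0.05, equal correlations, and A and B pooled against control. If 0.05 is one-sided, the excess remains: 14.3% at correlation 0 and 8.0% at 0.9, against 5%. Letting either set count adds to this by an amount the documents do not allow to be fixed.

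The sponsor should correct it. Confidence is medium, because the intended rule may be one that carries no inflation.

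**What to change.** Before any results are seen:

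1. In the primary endpoint, list the three outcomes of Statistical Methods and remove 'such as'.
2. Name one analysis set as decisive and use the other for sensitivity only.
3. Either name one of the three as the single primary outcome, or test the three NNS-versus-control comparisons with Holm at an overall two-sided 0.05 (smallest p against 0.0167, next against 0.025, last against 0.05).
4. Keep 5 versus 15 minutes as the secondary endpoint.
5. Under End of Study, make the significant result refer to this same definition.

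This defines the event that may end the study. It does not control the extra error from repeated looks at the data, which needs separate treatment.

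**Cost.** The edit is to wording, but the choice in step 3 has consequences. With Holm, the hypothetical 80% falls to 66% at the first step or 71% at the second. Restoring 80% at the first step would need about 33% more infants: ((2.394 + 0.842)/2.802)² = 1.33. With a single primary outcome, that outcome keeps its power, but the other two no longer decide success.

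### The 'ITT' set requires interventions that no untreated control can receive, the 'FAS' requires complete data, and no planned analysis keeps all 180 infants as allocated

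*Protocol*

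**What the plan says.** All the relevant text is in the protocol.

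- Section VI, Criteria for Evaluation, fixes two analysis sets. One is defined by exposure: "an intent-to-treat set (ITT) means data of a participant with at least 4 interventions was collected". The other is defined by completeness of the records: "The full analysis set (FAS) means all the data of a participant was collected".
- The same paragraph commits the analyses to them: "The primary and secondary endpoints will be analyzed by a FAS and an ITT". No third set is named, and neither definition has a separate rule for controls.
- Section VI, Endpoints, sets the primary comparison as NNS "compared to no intervention". The secondary comparison is 5 against 15 minutes of NNS.
- Section VI, Number of Planned Patients, gives "180 participants, 146 evaluable participants" and, in each of two gestational-age strata, "Experiment A group:30, Experiment B group:30, Control group: 30".
- Section IV, Study Rationale, says of feeding intolerance: "This symptom will result in less feeding or fasting".

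**The concern.** Intention-to-treat means that every participant is analysed in the group allocated, whatever was received. A minimum of 4 interventions is a rule on treatment received, so the definition contradicts its label. 'Full analysis set' normally names a set as close as possible to all those allocated; here it names infants with nothing missing. A reader of results labelled ITT and FAS would believe that everyone had been counted.

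Two consequences follow. First, the control group is untreated by design, so the 'ITT' rule has no literal meaning for it, and the primary comparison loses its comparator. Second, both rules can select on the outcome. NNS is given before feeds, and the rationale says intolerance leads to reduced or withheld feeding. An infant whose feeds stop before the fourth intervention leaves the 'ITT' set, and one whose stopped feeds leave a gap in the data leaves the 'FAS'. An infant whose feeds are only reduced, or are stopped after the fourth intervention, stays in the 'ITT' set. If such losses fall more on the NNS groups than on controls, NNS can look beneficial when it is not, and no analysis of all allocated infants is planned as a check.

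**Working it through.** **Counts from section VI, Number of Planned Patients**

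- Total: 2 strata × 3 groups × 30 = 180, which reproduces the stated figure.
- Controls: 2 × 30 = 60. NNS infants: 4 × 30 = 120.
- Expected not evaluable: 180 − 146 = 34, and 34/180 = 18.9%. The protocol ties this figure neither to an analysis set nor to intolerance. It states no dropout rate, so the origin of 146 cannot be rebuilt.

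**Who is in each set**

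| Set | Literal membership | Keeps all 180? |
|---|---|---|
| 'ITT' | At most 120 NNS infants, 0 of 60 controls | No |
| 'FAS' | Infants with complete data (about 146 if 'evaluable' means complete, an assumption) | Only if nothing is missing |

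**What the 'ITT' rule could do to the primary comparison**

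The protocol gives no intolerance rate and no number of feeds per day, so the following is an illustration. Assumptions: no true effect; one yes/no outcome per infant; intolerance rate p = 20%, 30% or 50%; a share e of NNS infants excluded; a share f of those excluded intolerant, either halfway between p and 100%, that is (1 + p)/2, or 100%.

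*Reading 1, literal.* There are no controls in the set, so the contrast is not estimable.

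*Reading 2, the same filter in all three groups.* The bias is 0 points and false positives stay at about 5%.

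*Reading 3, filter on the NNS groups only, all 60 controls kept.* The apparent NNS rate is (p − e·f)/(1 − e), and the spurious benefit is p minus that rate. The false-positive rate is the exact binomial probability that a two-sided pooled z-test (critical value 1.96) rejects, with 120(1 − e) NNS infants, rounded, against 60 controls.

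Worked example: p = 0.30, e = 0.05, so 6 of 120 are excluded and 114 remain.

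- f = 0.65: (0.30 − 0.0325)/0.95 = 28.2% against 30%, a spurious benefit of 1.8 points; 5.9% false positives.
- f = 1: (0.30 − 0.05)/0.95 = 26.3% against 30%, a spurious benefit of 3.7 points; 8.5% false positives.

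Ranges over p = 20 to 50%:

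| NNS infants excluded | Intolerant among the excluded | Spurious benefit (points) | False positives |
|---|---|---|---|
| 2% | all | 1.0–1.6 | 5–6% |
| 5% (6 of 120) | halfway | 1.3–2.1 | 5–7% |
| 5% (6 of 120) | all | 2.6–4.2 | 6–12% |
| 10% (12 of 120) | halfway | 2.8–4.4 | 6–12% |
| 10% (12 of 120) | all | 5.6–8.9 | 11–36% |

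The last row is an upper bound. With no filter the same test rejects about 5% of the time.

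**The case against.** The strongest reply is that the literal reading cannot be what was meant. The protocol assigns the primary comparison, which needs controls, to the 'ITT' set, so its authors must expect controls there. 'Interventions' probably stands for observed feeding sessions, loosely worded in an English synopsis. That is plausible, but the protocol does not say it. Even on that reading, infants with fewer than 4 sessions are dropped and the set is still not intention-to-treat.

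Other points stand as limits:

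- The control problem does not touch the secondary comparison, because both NNS groups receive interventions and the rule applies equally to them.
- Rates above 5% arise only if NNS infants are filtered and controls are not, which no text states. The 36% figure needs p = 20%, so 24 of 120 NNS infants are intolerant, and all 12 excluded must come from those 24. At 2% excluded the error rate is close to nominal.
- The planned analysis is GEE. If it uses repeated feed records, an infant with fewer than 4 interventions may contribute few of them, and dropping that infant may move the estimate less than in the illustration.
- The link from intolerance to exclusion is inferred from background text. How many infants would miss a fourth intervention in 3 days is unknown.
- At least 4 interventions is a minimum-exposure rule. Without the planned number of sessions it cannot be equated with full adherence.

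A separate analysis plan might add detail, but it does not answer the point: the protocol itself fixes both definitions and commits both endpoints to them.

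**Conclusion.** The concern holds, and the text needs correcting before analysis. That both sets are misdefined, that controls have no rule they can literally meet (0 of 60), and that neither set is defined to keep all 180 infants follow from the wording and the planned numbers alone. These points survive even if 'interventions' means observed feeds. 'As allocated' here means the planned A, B and control groups, since the document does not describe how allocation is made.

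The bias is less certain. It runs from none, with an equal filter, through the spurious benefits tabulated above, with a filter on NNS infants only, to a primary contrast that cannot be estimated on the literal reading. The illustrated figures rest on assumed rates and a simplified test; the finding does not depend on them.

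**What to change.** In section VI, Criteria for Evaluation:

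1. Define the main set, under whichever of the two names is kept, as every allocated infant in all three groups, analysed in the allocated group with all available feed records in the planned GEE. Require neither a minimum number of interventions nor complete data.
2. Keep the two current sets as supportive analyses only, under names that describe them: a minimum-exposure set and a complete-data set. Give the minimum-exposure set a matching criterion for controls, such as at least 4 observed feeds.
3. State in advance, here or in the analysis plan, how feeds not given enter each outcome. This is a useful companion to the change; the finding does not rest on its absence.

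The cost is two reworded definitions and one added sentence, with no extra infants or measurements. The estimated NNS effect may be smaller, because infants who received little NNS will count in their allocated group.

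### The stated GEE comparison covers NNS against no intervention only: the 5 vs 15 minute secondary contrast is not named, and the gestational-age band is left out of a design balanced within bands

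*Protocol*

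**What the plan says.** All of this is in the Protocol; no SAP is at hand.

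- **Endpoints (section VI).** The primary endpoint sets NNS against no intervention on gastric residual volume (GRV), meteorism and regurgitation. The secondary endpoint asks whether 5 minutes of NNS reduces the same three outcomes "better than 15 minutes of non-nutritive sucking before oral feeding".
- **Criteria for Evaluation (section VI).** "The primary and secondary endpoints will be analyzed by a FAS and an ITT".
- **Statistical Methods (section VI).** The secondary endpoint is mentioned once, in the sentence on the Kolmogorov-Smirnov normality check. The next sentence gives the only comparison: the difference "between the NNS intervention and no intervention will be analyzed by the generalized estimating equations", at an α of 0.05.
- **Number of Planned Patients (section VI).** "180 participants, 146 evaluable participants", in two gestational-age bands (26 to 27 weeks and 28 to 31 weeks, each plus 6 days). Each band has the same line: "Experiment A group:30, Experiment B group:30, Control group: 30".
- **Study Rationale (section IV).** "Generally, more early gestational ages and lower birth weight accompany more problems". Feeding intolerance, with GRV, meteorism and regurgitation as its examples, "is also increased due to an immature, less functional gastrointestinal tract".

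**The concern.** The Protocol promises an analysis of two contrasts and states one. An analyst who follows the GEE sentence literally, with a single indicator for NNS received or not, answers the primary endpoint and has nothing to report on duration. An analyst who enters three arms can answer both. The choice should be fixed before the data are seen, because the second experimental arm is needed to answer the duration question.

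The second part concerns efficiency. The plan goes to the trouble of equal arm sizes within each gestational-age band, and the rationale says that earlier gestation brings more problems. A model that ignores the band leaves the between-band difference in the residual variation. What is at stake there is interval width and power, not bias.

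**Working it through.** **1. The plan's own total.** 2 bands × 3 arms × 30 = 180, which reproduces the stated number and confirms equal arms within each band. The 146 evaluable infants imply a loss of 34, or 34/180 = 18.9%; the Protocol does not say how that figure arose, and nothing below depends on its origin.

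**2. Endpoints against the stated comparison.**

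| Endpoint | Contrast required | Named in Statistical Methods |
|---|---|---|
| Primary | NNS vs no intervention | Yes |
| Secondary | 5 min vs 15 min | No |

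**3. What each coding can estimate.** I take the two experimental arms to be the 5 and 15 minute arms. The Protocol states neither of the codings below.

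- Yes/no NNS: the design rows (intercept, NNS) are control (1,0), 5 min (1,1), 15 min (1,1). The rank is 2, and the fitted 5 minus 15 difference is (1,1) − (1,1) = 0 whatever the data show.
- Three-level arm: the rows are control (1,0,0), 5 min (1,1,0), 15 min (1,0,1). The rank is 3, and 5 minus 15 is the contrast (0,1,−1), which is estimable.

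**4. Leaving out the band (illustration).** Assumptions: one summary value per infant, a linear outcome, two-sided 0.05, and a band difference of d within-band SDs. The Protocol gives no value for d, so a range is shown.

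With half of each arm in each band, the variance within an arm is 1 + d²/4 when the band is ignored and 1 when it is in the model. The ratio of reported SEs is therefore √(1 + d²/4):

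- d = 0.25: √1.0156 = 1.008
- d = 0.5: √1.0625 = 1.031
- d = 1.0: √1.25 = 1.118

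With equal cells the band effect cancels from the arm contrast, so the true spread of the estimate does not change; only the reported SE is inflated. The type I error is then 2[1 − Φ(1.96·√(1 + d²/4))]. The power for a 0.5 SD difference with 60 vs 60 is Φ(0.5/√(2/60) − 1.96·√(1 + d²/4)), against 78.2% with the band in the model.

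| d (assumed) | Reported SE ratio | Type I error | Power, band omitted |
|---|---|---|---|
| 0.25 | 1.008 | 0.048 | 77.7% |
| 0.5 | 1.031 | 0.043 | 76.4% |
| 1.0 | 1.118 | 0.028 | 70.8% |

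**5. Allowing for losses.** Simulation of the 5 vs 15 minute contrast, with 34 of 180 infants lost at random regardless of arm and band and a three-level arm factor, gave reported-SE ratios of 1.007, 1.031 and 1.12. The true spread of the unadjusted estimate exceeded that of the adjusted one by less than 1% at d = 0.25 and 0.5, and by about 2% to 3% at d = 1.0. The type I error at d = 1.0 was about 0.034, still conservative.

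**The case against.** The strongest reply is that this is missing detail, not a mistake. The document is a synopsis. Arm coding, contrasts and covariates are usual SAP content, and a SAP may exist. The Protocol does state the secondary endpoint, its outcomes and its analysis sets; it lists three arms separately; and nothing in it excludes a GEE for duration. Most of this stands. A reader might infer that the planned analysis cannot tell which duration is better. The text does not support that: it follows only from a yes/no coding, which the Protocol does not state, and a three-level factor fits the wording equally well. The rationale's aim to "evaluate whether the different times of NNS before feeding can decrease the incidence of feeding intolerance" does not settle it either, since it can be read as each duration against none. What remains is that Statistical Methods does name a comparison, and that comparison matches only one of the two endpoints.

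On the band, the reply is that model terms are a choice, the bands are nowhere called randomisation strata, and a band term is not ruled out. That is right, and it is why this part is offered as an improvement. A reader might also take the 1%, 3% and 12% as information lost, or convert them into infants. They are inflation of the reported SE; with near-balanced bands the estimate itself is almost as precise without the band. Finally, one linear value per infant is a simplification of repeated outcomes, some of which may be yes/no.

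**Conclusion.** The point holds in limited form. The only GEE comparison stated matches the primary endpoint, and the 5 vs 15 minute contrast that the Protocol commits to analysing is not named. The gap lies in the wording and does not show that the analysis would fail: a correct analysis is compatible with the text but not fixed by it.

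Omitting the band is not an error. With balanced bands and a linear outcome it causes no expected bias; it makes intervals too wide and the test conservative. The cost is negligible if the bands differ by 0.25 SD and noticeable at 1.0 SD (reported SE about 12% too large; power about 71% instead of 78% in the example, with equal cells). Those sizes rest on assumed band differences and, where losses are allowed for, on losses unrelated to arm and band. The real size cannot be computed from the Protocol. The change is worth making because it is nearly free.

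**What to change.** In Statistical Methods, replace the single comparison with a model and two contrasts. Fit each GEE with arm as a three-level factor (control, 5 min, 15 min) and gestational-age band as a fixed term. From that model report (1) NNS vs no intervention, saying how the two NNS arms enter that comparison, and (2) 5 vs 15 minutes, each with an estimate and 95% interval.

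This costs about two sentences, no new data and no change in sample size, since arm and band are known for every infant. The model gains two parameters over a yes/no coding without band. If a logit link is used for a yes/no outcome, the plan should state that the odds ratio is conditional on band.

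### The protocol lets the sponsor stop early on any significant result, with no planned looks or adjusted threshold, so the stated 5% error rate does not hold and early-stopped estimates are on average too large

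*Protocol*

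**What the plan says.** The Protocol plans "180 participants, 146 evaluable participants", made up of two gestational-age strata, each with "Experiment A group:30, Experiment B group:30, Control group: 30". Under Statistical Methods, the comparison of non-nutritive sucking (NNS) with no intervention on gastric residual volume, meteorism and regurgitation "will be analyzed by the generalized estimating equations of SPSS 21", and "α value will be set at 0.05". No other significance level appears.

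Under End of Study the text reads "The sponsor may terminate the study due to the following situations". Item ii of the list that follows is "The data show a significant result to the hypothesis, although the recruited number does not reach 180". The section does not say when or how often the data may be examined, which limit an early result must pass, which of the three symptoms or which contrast must be significant, or who sees the interim data.

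**The concern.** Item ii is an early stop for efficacy that rests on significance alone. Each test of accumulating data at 0.05 gives chance another opportunity to produce a significant result, and the rule ends the trial when that happens. The 5% rate belongs to a single analysis; it is not a property of this design.

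The trial's main claim is at stake. If recruitment ends under item ii, the p-value and confidence interval are computed as if no earlier look had been taken, and the effect estimate has been selected for being large. The claim would also rest on fewer infants than the 180 planned. Treatment lasts 3 days and the study runs for two years, so outcomes arrive soon after enrolment and frequent looks are practicable. An unplanned stop cannot be repaired later, because a correction needs to know how many looks were taken and when.

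**Working it through.** **Inputs.** From the Protocol: 180 infants, three equal arms (30 per arm in each of two strata; 6 × 30 = 180), so NNS against control is 120 against 60; alpha 0.05. Assumed, because the Protocol does not say: a two-sided test, one outcome, equally spaced looks, and a stop at the first significant result.

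**1. The stated figure.** With one final analysis, 2 × (1 − Φ(1.96)) = 0.05. The stated alpha is correct in this case, and only in this case.

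**2. Repeated looks, no true effect.** At look k of K the statistic Z_k has correlation √(j/k) with an earlier Z_j. The overall error is P(|Z_k| > 1.96 for at least one k). With K = 2 the correlation is √(90/180) = 0.707 and the error is 8.3%. Simulation (400,000 runs) gives:

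| Looks at 0.05 | Two-sided error | Error in the favourable direction (nominal 2.5%) |
|---|---|---|
| 1 | 5.0% | 2.5% |
| 2 | 8.3% | 4.2% |
| 3 | 10.7% | 5.3% |
| 5 | 14.1% | 7.0% |
| 6 (every 30 infants) | 15.5% | 7.7% |
| 10 | 19.4% | 9.6% |

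Looking after every infant gives 19% starting from infant 60 and 25% starting from infant 30.

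**3. Confidence interval.** An uncorrected 95% interval excludes zero exactly when the test is significant. With no true effect its coverage is therefore one minus the error above: 100 − 8.3 = 91.7% with two looks and 100 − 14.1 = 85.9% with five.

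**4. Undefined trigger.** If any of the three symptoms may trigger the stop (correlation 0.3 assumed), a single final look already gives about 13.5%, which is multiplicity and not early stopping. Two, three and six looks raise it to about 22%, 28% and 38%. Only the rise above 13.5% is due to item ii.

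**5. Exaggeration.** Take a true effect that one final test would detect with 80% power. Average estimates as multiples of the truth are:

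| Looks | Trials stopped early | All significant trials | All trials |
|---|---|---|---|
| 1 (final only) | – | 1.12 | 1.00 |
| 2 | 1.40 | 1.23 | 1.10 |
| 5 | 1.46 | 1.40 | 1.26 |
| 10 | 1.56 | 1.53 | 1.39 |

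The median size at the end is 108 infants with five looks and 72 with ten.

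A smaller effect fares worse. The standard error of the standardised difference is √(1/120 + 1/60) = 0.158, so a true 0.20 SD gives an expected Z of 0.20/0.158 = 1.27 and only 24% power. Significant trials then report on average 0.53 SD with six looks, against 0.40 SD with one final test.

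**6. Limits that restore 5%.** A constant nominal threshold would have to be about p < 0.030 with two looks, 0.022 with three and 0.016 with five. O'Brien-Fleming limits for two looks are Z = 2.797 and 1.977, that is p = 0.0052 and 0.0480; simulated overall error is about 5.0%.

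**The case against.** The strongest reply is that the number and timing of looks and the boundaries commonly sit in an SAP, which is not at hand. The Protocol never says that interim tests use an unadjusted 0.05; that level is attached to the analysis in Statistical Methods. This does not rescue the rule. The Protocol goes beyond leaving details open: it fixes a stop on a bare significant result, in a document with one threshold. An SAP with proper boundaries would have to override that text.

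Several narrower points stand:

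- The sponsor may stop but need not. The figures assume a stop at every first crossing, and the very frequent schedules are illustrations. Discretion does not protect alpha, however, unless no looks are taken.
- The three-outcome figures include multiplicity that would remain with item ii deleted, and the text speaks of one hypothesis. The one-outcome figures carry the finding.
- The 0.20 SD case is unfavourable: with 24% power, even a single test doubles the average significant estimate (0.40 against 0.20). At 0.45 SD, with about 81% power, the averages are 0.64 with six looks and 0.50 with one. The bias is smaller but still present.
- Exaggeration is an average property; one particular stopped estimate need not be too large.
- Item i ("The master thesis topic is changed") does not depend on the data and does not inflate the error. It is no part of this finding.

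**Conclusion.** The concern holds and must be fixed. As written, the Protocol permits an unadjusted efficacy stop, and any added look at 0.05 puts the overall error above 5%. For one outcome tested two-sided, the error is about 8% with two looks, 14% with five and 19% with ten. With 80% fixed-design power, estimates from trials stopped early average 1.40 to 1.56 times the truth for two to ten looks. The direction is certain. The size depends on the assumed look schedule, on stopping at the first crossing and, for the bias, on the true effect, which the document does not state.

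**What to change.** Delete item ii and state that efficacy is analysed once, after 180 infants have been recruited and their data are complete. The stated 0.05 is then true for a single test. The cost is one wording change and the loss of ad hoc early stopping; no infants are added.

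If the sponsor wants an early efficacy stop, replace item ii with one planned interim on a single named outcome and contrast, using O'Brien-Fleming limits: two-sided p < 0.0052 at the interim and p < 0.0480 at the end. These limits assume that half the information is in. That is 90 of 180 infants, but since only 146 are expected to be evaluable, the trigger is better set at 146/2 = 73 evaluable infants. The text should also say who sees the interim result, rule out any other comparative look, and require an estimate and interval adjusted for early stopping. This costs a little more planning and a slightly stricter final threshold, within the 180 already planned.
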